The overall goal of our project, Accelerating Colorectal Cancer Screening and Follow-Up Through Implementation Science in Chicago (ACCSIS-Chicago), is to test a multilevel, multicomponent intervention to increase rates of CRC screening, follow-up, and referral-to-care among racial/ethnic minority and low-income populations in Chicago, Illinois. The ACCSIS-Chicago is a two-phase study. During the UG3 Planning-Exploratory Phase (Year 1), we conducted in-depth interviews with one of our FQHC partners in another similar study to understand how to best increase the adoption, implementation, and sustainment of a multilevel, multicomponent intervention, and use the information to develop implementation support strategies (IRB18-1141). In the UH3 Implementation Phase (Year 2 to 5), we will implement the multilevel, multicomponent intervention in four FQHCs using a stepped wedge design and evaluate the effectiveness using multilevel modeling.

Study Design/Setting/Participants:

In the UH3 Implementation Phase, we will have 4 clusters of clinics from four different FQHCs. Each cluster will have 5 to 12 clinics and a total of 20 to 35 primary care providers (internist, family practice physician, nurse practitioners, and physician assistants). We will implement our multilevel, multicomponent intervention in three phases. In phase 1, we will implement the provider education and community outreach component to target the provider- and community-level influences. In phase 2, we will add the mobile patient reminder, and the provider assessment and feedback components to target organization-level influences. In phase 3, we will add the CRC patient navigation component to address the possible barriers that individuals face during the processes of CRC screening and follow-up.

Study Intervention and Measures:

[figure not shown]
The multilevel intervention components will include 1) provider education, 2) provider assessment and feedback, 3) patient reminder using mobile platform, 4) patient navigation, and 5) community outreach. The first three components will be implemented as part of the quality improvement project at the partner FQHCs. During the first six months, we will collect baseline data at our partner FQHCs. After we start implementing the multilevel intervention, we will collect outcome data every three months until the completion of the 4-year study period. At the clinic and provider levels, we will work with the Quality Improvement Department to collect outcome data on 1) CRC screening rates, 2) CRC screening order rates, 3) CRC screening completion rates, 4) follow-up diagnostic evaluation rates, 5) follow-up diagnostic evaluation completion rates, and 5) time to completion of diagnostic evaluation. At the patient level, we will collect data on patient navigation service utilization and the satisfaction of the services.

1. BACKGROUND AND SIGNIFICANCE

1.1. Background

Colorectal Cancer Burden in Illinois

Colorectal cancer (CRC) is the second leading cause of cancer death in the United States. Screening for CRC not only detects the disease early when treatment is more effective but also prevents cancer by finding and removing precancerous polyps. Despite strong evidence to support CRC screening, nationally, only 65% of adults had up-to-date screening [1]. Residents in the state of Illinois are no exception, and in fact, Illinois ranks in the last quartile

(54% to 50%) for CRC screening rates across the nation, as shown in *Figure 1* [2]. This disturbing statistic has no doubt been a contributor to the high CRC incidence in Illinois. In 2013, Illinois had the 13th highest age-adjusted CRC incidence rate in the nation at 42.9/100,000 [2]. Among communities of color, African

American (AA) males and females in Illinois rank the 8th highest CRC mortality rate in the nation [3]. Furthermore, Illinois has the 5th largest number of Hispanic and Asian-American populations in the nation. Both Hispanic and Asian Americans have significantly lower CRC screening rates compared to Non-Hispanic White and Black [4].

Colorectal Cancer Burden in Cook County

Cook County is the most populous county in Illinois and the second-most populous county in the United States. According to the 2010 census, Cook County had 5,194,675 residents, who represented 40% of all residents in the state of Illinois. Furthermore, 24% of Cook County residents (or 1,253,354 individuals) were between the ages of 50 and 74 years in

2010 [5]. Although Cook County has a similar CRC incident rate as Illinois, its CRC mortality rate is significantly higher than the Illinois overall rate and ranks 3rd across the 102 counties in Illinois [5]. Some of Cook County's

Table 1: Population Estimates of Designated Regions in Illinois

	Illinois	Cook County	Chicago
Population*	12,875,255	5,231,351	2,695,598
NH White**	77.9%	65.9%	45.0%
NH Black**	14.8%	24.6%	32.9%
Hispanic**	16.3%	24.6%	28.9%
Asian***	4.7%	6.4%	5.5%
% Living below 200% of the poverty level	30.8%	35.2%	43%

* 2012 Population estimates from the U.S. Census Bureau.

** Race data may be above or below 100% due to estimate methodology that includes multi-racial individuals in each racial group.

*** 2009-2013 American Community Survey 5-Year Estimates.

population characteristics may contribute to the colorectal cancer burden. Compared to other counties in Illinois, Cook County has the most diverse population with significantly higher numbers of African Americans, Hispanics, Asian Americans, as well as people who are living below 200% of the poverty level (*Table 1*) [5]. Studies have consistently shown that racial and ethnic minorities, as well as those living in poverty, suffer disproportionately from health disparities, and the 2010 National Health Interview Survey (NHIS) found that CRC screening rates were significantly lower among racial/ethnic minorities compared to whites (59.8%), Blacks (55.0%), Hispanics (46.5%) and Asians (46.9%) [6]. The low socioeconomic indicators and poor CRC health outcomes experienced by a disproportionate number of Cook County residents underscore the critical need to create a more organized approach to CRC prevention and control in the county. Cook County is also home to the City of Chicago, where approximately 54% of county residents reside. Chicago is the 3rd most populous city in the U.S., and its CRC mortality rate overall is 21.5 deaths per 100,000, higher than the nation's overall colorectal cancer mortality rate of 17.5 deaths per 100,000. Chicago also has the 2nd largest African American population, 4th largest Hispanic population, and 5th largest Asian American population in the nation. Although efforts have been in place to improve CRC outcomes in Chicago and Cook County, the lack of coordination across different sectors and attention to multilevel influences diminish the impact of such efforts.

Safety-Net Health Care Systems and Colorectal Cancer Control

Although the percentage of the U.S. adult population that is up-to-date with recommended CRC screening increased from 54% in 2002 to 65% in 2010 [7], nearly 28% of the eligible adults still had never been screened [2]. Individuals who were without health insurance and a regular care provider were more likely to have never been screened than those with health insurance and with a regular care provider [2]. Racial/ethnic minorities and low social, economic status (SES) populations are among those who lack health insurance and a usual source of care. Underuse of CRC screening is frequent among these populations [8-10], who disproportionately receive health care in safety-net settings, such as federally qualified health centers (FQHCs) [7, 11]. FQHCs are designed to provide comprehensive, quality primary health care services to medically underserved communities and vulnerable populations. In 2016, FQHCs served 26 million patients, of whom 23% were uninsured, 62% were racial/ethnic minorities, and 92% were living below 200% poverty level [12]. Because many of our nation's most disadvantaged and vulnerable individuals make use of FQHCs to obtain health care, FQHCs play a significant role in CRC prevention and control.

1.2. Significance

The overall goal of our project, ***Accelerating Colorectal Cancer Screening and Follow-up through Implementation Science in Chicago (ACCSIS-Chicago)***, is two-fold: 1) to understand how to best increase the adoption, implementation, and sustainment of evidence-based interventions; and 2) to provide the evidence base for multilevel interventions that increase rates of CRC screening, follow-up, and referral-to-care among racial/ethnic minority and low SES populations. The ACCSIS-Chicago will focus on Cook County geographically, especially in Chicago, where 54% of the Cook County population resides. We will partner with local FQHCs, community-based organizations, and workplaces to increase rates of CRC screening, follow-up, and referral-to-care among racial/ethnic minority and low SES populations. The ACCSIS-Chicago project will use two types of implementation strategies to increase rates of CRC screening, follow-up, and referral-to-care among racial/ethnic minority and low SES populations: 1) a multilevel intervention, which will have multiple components, and 2) implementation support strategies to accelerate the adoption, implementation, and sustainment of the multilevel intervention. In the UH3 Implementation Phase, we will partner with 4 FQHCs, which have 35 clinics in the Chicago area and provide primary care service to racial/ethnic

minority and low SES populations. Together, these 4 FQHCs served more than 188,037 patients in 2016. We will use a stepped wedge cluster randomized trial design to examine the effectiveness and impact of our multilevel interventions on increasing rates of CRC screening, follow-up, and referral-to-care across these 4 partner FQHCs. We will also implement a local innovation, ILColonCARES Program, and assess its feasibility and effectiveness on the follow-up of a positive FIT.

2. STUDY OBJECTIVES, DURATION, AND STUDY SITES

2.1. Study Objectives

Objective 1: *Collect baseline data during the first 6 months before implementing any intervention component.*

Objective 2: *Implement the intervention in three phases: 1) provider education plus community outreach; 2) add provider assessment and feedback + patient reminder; and 3) add a CRC navigator program.*

Objective 3: *Create a grand model to test the overall effectiveness of the multilevel intervention on primary outcomes within and across levels, as well as separate models to assess effectiveness at each phase.*

Objective 4: *Identify potential interaction or mediation effects and assess such effects on primary outcomes.*

Exploratory Objective 5: *Implement a local innovation, IL ColonCARES Program, and assess its feasibility and effectiveness on the follow-up of abnormality.*

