2.2. Study Duration and Study Sites

The ACCSIS – Chicago UH3 Implementation Phase will last for four years (November 2019 to October 2023). In the UH3 Implementation Phase, we will have 4 clusters of clinics from four different FQHCs. Each cluster will have 5 to 12 clinics and a total of 20 to 35 primary care providers (internist, family practice physician, nurse practitioners, and physician assistants). Table 1 summarizes the characteristics of our FQHC partners. Together, our

Table 1: Characteristic of Partner Health Care Systems

	Total Patients	% of Racial Minority	% at or below 200% poverty	% of Uninsured	CRC Screening Rate	Adjusted Quartile Ranking on CRC Screening ¹	No. of Clinics ²	No. of Providers
PCC Community Wellness Center	48,357	92.2%	93.1%	9.3%	30.0%	Quartile 4	11	60
Aunt Martha's Youth Service Center, Inc.	51,343	80.9%	96.2%	16.5%	32.9%	Quartile 3	12	21
Lawndale Christian Health Center	51,235	96.9%	97.6%	30.2%	35.0%	Quartile 2	5	35
Near North Health Service Corporation	37,102	94.6%	97.3%	35.1%	31.0%	Quartile 3	7	20

1. Adjusted Quartile Ranking provides a health center's adjusted quartile ranking compared to health centers nationally for each of the clinical performance measures. Clinical performance for each measure is ranked from quartile 1 (highest 25% of reporting health center) to quartile 4 (lowest 25% of reporting health centers).

2. Reported by partner health care system.

partner FQHCs served 188,037 patients in 2016, and at least 10% of these patients were ≥ 50 years old. It is important to point out that three of our partners' CRC screening rates were in the lower third and fourth quartiles compared to other FQHCs in the nation, indicating room for improvement. We will continue to monitor their ranking throughout the study.

[figure not shown]

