3. STUDY DESIGN AND PROCEDURES

3.1 Study Design

We will use a stepped wedge cluster randomized trial design to assess the effectiveness of our proposed multilevel intervention. Although it will be preferable to use a traditional cluster-randomized trial to test our multicomponent, multilevel intervention, we will need a larger number of clusters, which will be more expensive and infeasible. Also, it is unacceptable for our partner(s) assigned to a control group to not benefit from well-studied evidence-based interventions. Since the stepped wedge design retains some elements of randomization and has the advantage for multiple data collection points over a long period and allows clusters to act as their own control, it is the best alternative to the gold standard.

In the UH3 Implementation phase, we will partner with four FQHCs. We will randomize the four FQHCs to either group 1 or group 2. The biostatistician will conduct the randomization independently from the research team. The difference between the two groups is that group 2 will start the implementation later. We will implement our multilevel intervention in three phases. In phase 1, we will implement the provider education and community outreach component. In phase 2, we will add the mobile patient reminder and the provider assessment and feedback components. In phase 3, we will add the CRC patient navigation component. Figure 1 shows our stepped wedge study design.

Figure 1: Stepped Wedge Study Design.

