3.5 Data Sources

During the first three months, we will work with the Quality Improvement Department at each partner site to collect baseline data on primary outcomes through the existing electronic medical record or chart reviews. After we start implementing the multilevel intervention, we will collect primary outcome data each quarter until the completion of the 4-year study period. Table 2 summarizes the primary outcome measures.

Table 2. Outcome Measures for the Multilevel Intervention

Outcome	Operational Definition	Data Sources	Data Collection Period	Level of Data Analysis
Patient CRC screening rates	Numerator: # of patients completed CRC screening Denominator: # of patients eligible for CRC screening	• EMR • Chart reviews as needed	Every quarter	Level 2, Level 3, Level 4
CRC ordering rates	Numerator: # of patients received order for CRC screening Denominator: # of patient eligible for CRC screening	• EMR • Chart reviews as needed	Every quarter	Level 2, Level 3, Level 4
Patient notification rates (FOBT/FIT +)	Numerator: # of patients notified Denominator: # of patients had FOBT/FIT +	• EMR • Chart review as needed	Every quarter	Level 2, Level 3, Level 4
Time to notification of positive results	# of days between notifying a patient with a positive result and the result available to the provider	• EMR • Chart reviews as needed	Every quarter	Level 2, Level 3, Level 4
Follow-up diagnostic evaluation referral rates	Numerator: # of patients received referral for evaluation Denominator: # of patients had FOBT/FIT +	• EMR • Chart reviews as needed	Every quarter	Level 2, Level 3, Level 4
Time to referral for follow-up diagnostic evaluation	# of days between the referral and the result available to the provider	• EMR • Chart reviews as needed	Every quarter	Level 2, Level 3, Level 4
Follow-up diagnostic evaluation completion rates	Numerator: # of patients completed diagnostic evaluation as ordered Denominator: # of diagnostic evaluation referral made	• EMR • Chart reviews as needed	Every quarter	Level 2, Level 3, Level 4
Time to completed diagnostic evaluation	# of days between the positive FOBT/FIT result available to the provider and the completion of the diagnostic evaluation	• EMR • Chart reviews as needed	Every quarter	Level 2, Level 3, Level 4

* Level 2 = Provider level; Level 3 = Clinic level; and Level 4 = organization level.

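### The window before any FQHC is exposed is one or two quarters and the sections disagree on which; earlier EMR quarters would allow a coarse trend check, provided the model has quarter and FQHC effects

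*Combined protocol and SAP*

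**What the plan says.** The plan gives the baseline three times. The study summary has "During the first six months, we will collect baseline data at our partner FQHCs", and Objective 1 in section 2.1 agrees: "Collect baseline data during the first 6 months before implementing any intervention component". Section 3.5 differs: "During the first three months, we will work with the Quality Improvement Department at each partner site to collect baseline data on primary outcomes". The source named there is "through the existing electronic medical record or chart reviews". Once implementation starts, "we will collect primary outcome data each quarter until the completion of the 4-year study period".

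Section 3.1 randomises four FQHCs to two groups that differ only in start time. It justifies the design partly because it "has the advantage for multiple data collection points over a long period and allows clusters to act as their own control". The step timing is in Figure 1, which is not shown in the text available.

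No section states how far back the extraction reaches, plans quarters before the study start, or compares the groups' pre-intervention trends. The models in section 4 have random effects for clinic and provider. They contain no calendar-time term and no FQHC effect.

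**The concern.** With two groups of FQHCs, a phase effect is estimated from the gap between the groups while one is a phase ahead, set against their gap when both are in the same phase. The only same-phase quarters free of any intervention effect are those before the first start. One quarter gives a level and no slope. Two give a single change per FQHC and cover half a calendar year, so trend, season and noise cannot be told apart.

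Calendar-quarter effects would absorb a season or trend that both groups share. They would not absorb one that differs between the groups. If the group randomised to start first was already improving faster, that would look like an intervention effect, and the planned data could not show it. A random allocation of four FQHCs cannot be relied on to balance trends: a 2:2 split (assumed) has only 6 possible assignments.

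**Working it through.** The plan states no power, precision or effect size, so it has no figure to reproduce.

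**Inputs from the plan.** Four FQHCs, two groups, three cumulative phases, quarterly outcomes, and four years (16 quarters). The baseline is 2 quarters (section 2.1) or 1 (section 3.5).

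**Assumed.** Two FQHCs per group; 14 quarters after the first start; phase length/delay of group 2 of 3/2, 3/3, 4/2 or 4/4 quarters; and a model with FQHC and quarter effects.

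**1. Trend check.** With n equally spaced, independent quarters, the variance of a slope is proportional to 1/[n(n²−1)/12].
- n = 2: 2×3/12 = 0.5
- n = 8: 8×63/12 = 42
- n = 10: 10×99/12 = 82.5

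The SE of the slope difference falls by 1 − √(0.5/42) = 89% with eight quarters, and by 1 − √(0.5/82.5) = 92% with ten. Across constant, decaying and mixed correlation structures, the fall with ten quarters was 71-92%. With one quarter no slope can be estimated.

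The check stays coarse. With ten quarters the SE was 0.14-1.5 points per quarter under the assumptions tried. Two against two FQHCs leave about 2 degrees of freedom (t = 4.30), so only divergences above about 4.30×0.14 = 0.6 to 4.30×1.5 ≈ 6.5 points per quarter would stand out. Eight quarters are somewhat coarser.

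**2. Precision, uncorrelated noise.** Let b be the number of baseline quarters, L the quarters in which group 1 is one phase ahead (equal to the delay here), and S the later same-phase quarters. In units of the variance of one quarter's gap:
- one phase effect: 1/L + 1/(b+S)
- sum of the three: 3/L + 9/(b+S)

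| Phase/delay | L | S | One phase, b = 2 → 8 | SE fall | Sum, b = 2 → 8 | SE fall |
|---|---|---|---|---|---|---|
| 3/2 and 4/2 | 2 | 8 | 0.600 → 0.5625 | 3.2% | 2.400 → 2.0625 | 7.3% |
| 3/3 | 3 | 5 | 0.476 → 0.410 | 7.2% | 2.286 → 1.692 | 14.0% |
| 4/4 | 4 | 2 | 0.500 → 0.350 | 16.3% | 3.000 → 1.650 | 25.8% |

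For example, 4/4: 1 − √(0.350/0.500) = 16.3% and 1 − √(1.650/3.000) = 25.8%.

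**3. Precision, autocorrelated noise** (generalised least squares, AR(1), same layouts). At 0.5 the falls are 0.5-7.7% per phase and 1.5-10.8% overall. At 0.8 they are 0-1.1% and 0.1-1.4%.

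**4. Weight of the baseline gap in the overall effect.** This is 3b/(b+S). With b = 2 it is 6/10 = 0.6 (3/2 and 4/2), 6/7 = 0.86 (3/3) and 6/4 = 1.5 (4/4). It reaches 3 only when S = 0, that is, when the delay equals the phase length and the final quarters are discarded.

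**5. The models in section 4, with no time term.** Under a secular trend of 1 point per quarter, a within-FQHC comparison of b baseline quarters with p phase 1 quarters is biased by (b+p)/2 in group 1. With p = 3 this is 2.5 points for b = 2 and 5.5 for b = 8. Going from 2 to 8 quarters adds (8−2)/2 = 3 points whatever p is. In the fitted pooled model (delays of 2 or 4, phases of 2 to 4 quarters), the phase 1 bias is 2.5-4.3 points with 2 baseline quarters and 6.5-8.1 with 10.

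**The case against.** Several points on the other side have force.

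- **Look-back is not stated.** A reader might infer that only three or six months of records will ever be used. The documents say when baseline data are collected and are silent on how far back the records reach. Group 2 also stays unexposed for longer than group 1. What stands is that the jointly unexposed window is one or two quarters and no earlier data are planned.
- **The precision gain is not assured.** A reader might infer that more baseline will clearly sharpen the phase effects. The 16% and 26% need the 4/4 layout and no autocorrelation; other plausible settings give next to nothing. This objection stands.
- **The baseline gap does not dominate.** It is tempting to say that its error enters the overall effect three times. That needs the final quarters to be discarded, and section 3.5 plans to collect to the end. When the delay is shorter than the phase, there are also same-phase quarters in mid-study. The weight is 0.6 to 1.5 in the layouts examined.
- **Randomisation.** Parallel trends are not an identifying assumption here as they would be without randomisation. That is right in principle, but it offers little reassurance in a single allocation of four units.
- **Feasibility.** Table 2 allows chart review for every outcome, and section 3.2.1 reports poor recording of FIT results in the EMR. Older quarters could mix changes in documentation with changes in screening. This limits which outcomes and quarters are usable.

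**Conclusion.** The concern holds in a limited form. The sections contradict each other on baseline length, and on either figure the jointly unexposed window is too short to distinguish a difference in season or trend between the groups from noise. Earlier quarters would make a descriptive check possible; that conclusion held under every correlation structure tried.

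The precision benefit is secondary: about 0-16% per phase and 0-26% overall for eight quarters instead of two. It rests on assumed step timing, a 2:2 split, and a model with quarter and FQHC effects that the plan does not contain. In the models as written, the same data would increase bias from a secular trend.

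A reader might go further and infer that the own-control argument fails, or that a longer baseline would rescue the design. The documents support neither. Same-phase quarters after the start also carry information if effects stay constant, and no amount of history changes the number of randomised units.

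**What to change.** - State one baseline length, the same in the study summary, Objective 1 and section 3.5.
- For all four FQHCs, extract the Table 2 outcomes that the EMR can supply for about eight quarters before the first phase 1 start. Use the same definitions, include only quarters in which EMR definitions and documentation were stable, and add no chart review. Confirm this for each FQHC and outcome.
- Add calendar-quarter and FQHC effects to the section 4 models, and enter the earlier quarters as control periods only in models that have both.
- Prespecify a plot of the two groups' pre-intervention trends, made before any effect is estimated and labelled descriptive.

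The cost is a longer one-time query, possibly a change to the IRB scope, and the loss of quarters affected by EMR changes.
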